10.8.3 Secondary and Exploratory Analyses

Sexual behavior and vaginal hygiene practice

The behavior measures will be collected via ACASI at the Enrollment Visit, follow-up visits, and at the 16-Week/Study Termination Visit. The sexual behaviors and vaginal hygiene practices include the number of sexual partners in the past 3 months, the number of new partners (not asked at enrollment), frequency of sex in the past 7 days, condom use in the past 7 days, condom use during the last sex act, anal sex in the past month, condom use during anal sex in the past month, and vaginal hygiene practices (list of various items/products inserted) in the past 7 days.

For each of the longitudinal behavioral measures, the mean (or the percentage if binary) in each visit in each arm will be computed and tabulated. The generalized estimation equation (GEE) method will be used to assess the difference of each measure between the two arms, accounting for within-subject correlation.

Acceptability

To assess acceptability of the study IVR, the number and percentage of participants in the study IVR arm experiencing at least one negative report of acceptability, including genitourinary discomfort, ring insertion/removal issues, expulsions, and/or changes in participant and/or partner sexual feeling during follow-up will be presented. This binomial proportion will be used to assess the acceptability of the study IVR along with its corresponding 95% confidence interval.

The above acceptability analysis will be supplemented by presenting the above proportion by site along with its corresponding 95% confidence interval.

Vaginal Flora

In order to assess the effect of the study IVR on the vaginal flora of sexually active, HIV-uninfected women, clinically significant changes in vaginal flora will be evaluated by the Nugent score with shift tables from baseline (Enrollment) to follow-up visits at week 4, 8, 12, and 16 to assess the effect on vaginal flora.

The Nugent score is graded 1 to 10 as follows:

- | | |
|------------------|---------|
| 1. Normal, | 0 to 3 |
| 2. Intermediate, | 4 to 6 |
| 3. BV, | 7 to 10 |

Any shift from normal at baseline to intermediate or BV at a follow-up visit, or intermediate or BV at baseline to normal at a follow-up visit, will be considered a clinically meaningful change in vaginal flora. The proportion of changes within each arm will be reported and will be formally compared using the Fisher exact test (from the

derivation of the two-sample case of the McNemar's test of change). Please refer to Levin and Serlin⁶⁸ for more details. In addition, this analysis will be supplemented by an analysis using the change from baseline in Nugent score for each woman. Comparison for differences in change from baseline between arms will be assessed by using an unpaired t-test or a Mann-Whitney test (if distribution of change scores does not allow the use of the unpaired t-test).

In addition to looking at shifts in the Nugent score and changes in biomarkers, within arm descriptions, and between arm comparisons will be done to assess clinically meaningful changes in quantitative measures of vaginal flora (defined by more than ≥ 1 log change in dominant members of the microflora) and to assess differences in the quantitative levels of these flora between arms during follow-up. Note that this analysis can only be performed using women from the US sites since quantitative cultures will not be conducted for women at the India site.

Biofilms

In the US sites, the percentage of women with biofilms on study IVR surface after 12 weeks of use will be computed for the IVR arm.

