3.2 Secondary Objectives

- Describe changes in sexual behavior and changes in vaginal hygiene practices in the study IVR vs. no IVR group over 12 weeks of use/non-use
- Evaluate the acceptability of the study IVR in HIV-uninfected women over 12 weeks of use
- Measure vaginal flora characteristics, and descriptively examine changes in these characteristics over the course of study IVR use

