6 STUDY PRODUCT

6.1 Regimen

Study participants will be randomized to either Group A to receive the study IVR or Group B to receive no study IVR (see Table 3). Participants in Group A will receive instructions on study IVR insertion and use and will then self insert (or by clinician if necessary), the study IVR at the Enrollment Visit. The study IVR should remain in place for 12 consecutive weeks. The study IVR will be removed by the study clinician/designee at the 12-Week Visit. Follow-up will continue for an additional 4 weeks after the final removal of the study IVR.

Table 3: Study Regimen

Group	N	Group Description
A	168	IVR for 12 consecutive weeks
B	84	No IVR for 12 consecutive weeks

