7.8.2 Acceptability and Behavioral Change

Acceptability will be measured via questions about ease of insertion and removal, feeling the study IVR during daily activities and sex, partner awareness of the study IVR during sex, partner attitude towards the ring, and willingness to use an HIV protective ring in the future, if one were available. Behavioral change potentially related to study IVR use will be assessed via comparisons between sexual activity and vaginal hygiene at enrollment and at follow-up visits, and via comparisons of sexual activity and vaginal hygiene between the study IVR arm and no ring arm.

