10.2.2 Study Secondary Endpoints

Consistent with the secondary study objectives to describe the changes in sexual behavior and changes in vaginal hygiene practices, to evaluate the acceptability of the study IVR, and to measure vaginal flora characteristics, and changes of these over the course of study IVR use, the following endpoints will be assessed:

- Per participant report, changes in sexual behavior and vaginal hygiene practices
- For women randomized to the study IVR arm, participant report of acceptability including genitourinary discomfort, ring insertion/removal issues, expulsions (including context of expulsion), and changes in participant and partner sexual feeling
- Changes in vaginal flora from enrollment to week 12 as measured by Gram stain Nugent score and quantitative culture (Note that these quantitative vaginal cultures will only be available from the US sites, therefore reducing the available sample size for this objective)

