10.4.5 Sexual Behavior and Vaginal Hygiene Practice

The behavior measures will be collected via ACASI at the Enrollment Visit, follow-up visits, and at the 16-Week/Study Termination Visit. The sexual behaviors and vaginal hygiene practices include the number of sexual partners in the past 3 months, the number of new partners (not asked at enrollment), frequency of sex in the past 7 days, condom use in the past 7 days, condom use during the last sex act, anal sex in the past month, condom use during anal sex in the past month, and vaginal hygiene practices (list of various items/products inserted) in the past 7 days.

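### The behaviour GEE in Protocol 10.8.3 compares arm levels and is not tied to the objective of change over 12 weeks of use; separately, the 3-month partner item reaches back before randomization.

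*Protocol*

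**What the plan says.** Protocol 3.2 sets the secondary objective: "Describe changes in sexual behavior and changes in vaginal hygiene practices in the study IVR vs. no IVR group over 12 weeks of use/non-use". The matching endpoint in 10.2.2 is "Per participant report, changes in sexual behavior and vaginal hygiene practices". Both are about change.

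On data collection, 10.8.3 states: "The behavior measures will be collected via ACASI at the Enrollment Visit, follow-up visits, and at the 16-Week/Study Termination Visit". By Appendix I that is Enrollment and weeks 4, 8, 12 and 16. The items listed in 10.4.5 and 10.8.3 have different recall windows. Most cover 7 days, the last sex act or a month, but one is "the number of sexual partners in the past 3 months". The number of new partners is not asked at Enrollment.

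On analysis, 10.8.3 has the mean or percentage tabulated for each visit and arm, and then: "The generalized estimation equation (GEE) method will be used to assess the difference of each measure between the two arms, accounting for within-subject correlation".

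On exposure, 6.1 says "The study IVR should remain in place for 12 consecutive weeks" and "Follow-up will continue for an additional 4 weeks after the final removal of the study IVR".

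**The concern.** The named contrast is the measure itself, compared between arms. The objective is change during the 12 weeks of use. The sentence applies to measures that the same section defines as collected at a visit before ring use, three visits during it and one visit four weeks after it. It neither selects among these visits nor says how the Enrollment value enters the between-arm comparison.

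Elsewhere the statistical section is more careful. In 10.8.3 the supplementary Nugent analysis compares change from baseline between arms, and the quantitative flora levels are compared during follow-up. In 10.8.2 the adherence analysis is limited to the first 12 weeks.

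The partner-count item raises a separate problem. A 3-month window asked every four weeks mixes time before and after randomization at the early visits, whatever model is chosen.

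Comparing behaviour and hygiene between the arms is one of the stated reasons for having a no-IVR arm (2.7.2, Study Design; 10.6). An attenuated between-arm estimate could be read as evidence that ring use does not change behaviour.

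**Working it through.** The Protocol gives no effect size, power or correlation for the behaviour measures, so there is no stated figure to reproduce.

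**Inputs from the Protocol.** Visits at weeks 0, 4, 8, 12 and 16 (10.8.3, Appendix I); ring in place during weeks 0 to 12, then 4 weeks without it (6.1); recall windows (10.4.5); 168 and 84 women per arm (10.4.1).

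**Assumptions.** Visits on their nominal dates; complete data; an effect d that starts at once, is constant and ends at removal; differences on the mean scale; for the 3-month item, an effect in proportion to the share of the window spent on the ring. Three months is taken as 13 weeks, with 12 weeks as the alternative.

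**Step 1: pooled effect, short windows.** The share of the effect kept is the weighted average of the on-ring share of the window at each visit. A single arm effect under independence or exchangeable correlation weights the visits equally.

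- Five visits: (0 + 1 + 1 + 1 + 0)/5 = 0.60, so 40% is lost.
- Four post-randomization visits: (1 + 1 + 1 + 0)/4 = 0.75, so 25% is lost. For new partners this is the most that can be pooled.
- Weeks 4, 8 and 12: 3/3 = 1, so nothing is lost (up to about 3% for past-month items if a month is 4.35 weeks).

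The weights depend on the working correlation. Under AR(1) with correlation 0.3, 0.5 and 0.7, the five-visit loss for 7-day items is 49%, 57% and 69%.

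**Step 2: the 3-month item.** The pre-randomization share at week w is (13 − w)/13. At week 16 the window runs from week 3 to week 16, and weeks 3 to 12 are on the ring.

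| Visit | Before randomization | On ring | After removal |
|---|---|---|---|
| Week 4 | 9/13 = 69% | 4/13 = 31% | 0 |
| Week 8 | 5/13 = 38% | 8/13 = 62% | 0 |
| Week 12 | 1/13 = 8% | 12/13 = 92% | 0 |
| Week 16 | 0 | 9/13 = 69% | 4/13 = 31% |

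- Weeks 4, 8 and 12 pooled: (4 + 8 + 12)/(3 × 13) = 24/39 = 0.62, so 38% is lost. With a 12-week window: 24/36 = 0.67, so 33% is lost.
- Five visits pooled: (0 + 4 + 8 + 12 + 9)/(5 × 13) = 33/65 = 0.51, so 49% is lost. With a 12-week window: 32/60 = 0.53, so 47% is lost.

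Dropping Enrollment and week 16 therefore does not cure this item.

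**Step 3: what attenuation would cost (illustration only).** Assume two-sided 0.05, exchangeable correlation ρ = 0.5 and, in SD units, variance of the arm difference over m visits = [(1 + (m − 1)ρ)/m] × (1/84 + 1/168). An effect of 0.306 SD gives 80% power on weeks 4 to 12. The same effect gives about 58% power with week 16 pooled in, and about 43% with Enrollment pooled in too. With ρ from 0.3 to 0.7, and the effect reset each time to give 80% power on weeks 4 to 12, the last figure runs from 46% to 41%.

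**The case against.** The strongest reply is that the Protocol does not specify the model being criticised. The visit list says when data are collected, not which visits are GEE responses. A GEE with an arm-by-visit term, or one on change from Enrollment at weeks 4 to 12, fits the same sentence and loses nothing for short-window items. Such detail often belongs in the SAP, which is not at hand. This stands as far as the model is concerned. A reader might infer that the GEE does pool all five visits and that any ring effect is cut by about 40%, but the text does not say so.

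Nor is Enrollment ignored. Section 7.8.2 describes how behavioural change is to be judged: "comparisons between sexual activity and vaginal hygiene at enrollment and at follow-up visits, and via comparisons of sexual activity and vaginal hygiene between the study" (the sentence ends by naming the two groups). Section 10.8.2 provides within-arm tests of change from baseline. A reader might infer that the Enrollment value is never used as a baseline, and these sections contradict that. They do not, however, join the two comparisons into a between-arm comparison of change.

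The 40% is also narrow. It does not apply to new partners, owes nothing to the 3-month window, and needs equal weights and an effect that ends at removal. Habits may persist to week 16, and for the 3-month item week 16 is mostly on-ring time.

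Finally, the objective is descriptive, and the by-visit tables will show weeks 4, 8 and 12 unpooled. That limits the harm. The mismatch between contrast and objective remains, as does the 3-month window, which no choice of model removes.

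**Conclusion.** The point holds in a limited form. The one formal between-arm analysis of behaviour is stated as a comparison of levels. It is not tied to change over 12 weeks of use: Enrollment has no baseline role in that test, and the off-ring week-16 visit is not separated.

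The size is conditional. If visits were pooled with equal weight and the effect existed only during ring use, items looking back a month or less would keep 60% of it over five visits, or 75% over the four post-randomization visits. An arm-by-visit or change-from-Enrollment model would avoid this.

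The look-back problem is separate and does not depend on such a choice of model. At weeks 4 and 8 the 3-month partner item covers about 69% and 38% pre-randomization time. Limiting the analysis to weeks 4 to 12 would still leave about 33 to 38% dilution, given the proportional-share assumption.

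All of this is confined to a secondary, descriptive objective. The primary safety and adherence conclusions are unaffected.

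**What to change.** Amend the GEE sentence in 10.8.3 to state that:

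- the response is the measure at weeks 4, 8 and 12;
- the covariates are the Enrollment value, where collected, and site. New partners would have site only. Site is there because 10.5 stratifies randomization by it; it does not itself address dilution;
- the arm effect is estimated over those three visits, and week 16 is reported separately;
- for partners in the past 3 months, the arms are compared at week 12 only, where about 92% of a 13-week window is on-ring (all of a 12-week window).

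The cost is analysis wording only. The data, visits and sample size stay as they are. Rewording the partner item at follow-up to ask about the time since the last visit would let weeks 4 and 8 contribute, but that changes one ACASI question and is optional.

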10.4.4 Changes in Vaginal Flora and Biomarkers

Changes in Nugent scores will be assessed by comparing the Nugent score at enrollment with the one observed at 12 weeks. An abnormal Nugent score is defined as a Nugent score higher than 3 while a normal Nugent score is defined as a score of 3 or less. The proportion of changes between enrollment and week 12 from normal to abnormal will be compared as well as the one from abnormal to normal.

Changes in Nugent score over time are naturally occurring. Based on a sample of 1016 women,⁶⁶ 28.4% of women with a normal Nugent score at enrollment had an abnormal Nugent score 4 months later while 32.8% of women with an abnormal Nugent score at enrollment had a normal Nugent score 4 months later. Therefore, for the purpose of power calculations, we are estimating the proportion of changes in Nugent scores from enrollment to week 12 at 30% in the no IVR arm and this for both from normal to abnormal and from abnormal to normal. Furthermore, we are estimating that 55% and 45% of women will be normal and abnormal, respectively, at enrollment.

The proportion of women with a change in Nugent score from normal to abnormal, at enrollment and 12 weeks, respectively, will be compared between the study IVR and no IVR arms. Assuming that the true proportion of changes in the no IVR arm is 30%, a sample size of 252 women (138 normal women at enrollment and available for the analysis) with a 2:1 randomization will allow detection of an absolute difference of 25% with 80% power (i.e. 30% of women in the no IVR arm and 55% of women in the study IVR arm).

Similarly, the proportion of women with a change in Nugent score from abnormal to normal, at enrollment and 12 weeks, respectively, will be compared between the study IVR and no IVR arms. Assuming that the true proportion of changes in the no IVR arm is 30%, a sample size of 252 women (114 abnormal women at enrollment and available

for the analysis) with a 2:1 randomization will allow detection of an absolute difference of 28% with 80% power (i.e. 30% of women in the no IVR arm and 58% of women in the study IVR arm).

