In addition to looking at shifts in the Nugent score, within arm descriptions, and between arm comparisons, will be done to assess clinically meaningful changes in quantitative measures of vaginal flora (defined by more than ≥ 1 log change in dominant members of the microflora) and to assess differences in the quantitative levels of these microflora between arms during follow-up. Quantitative vaginal cultures and vaginal biomarkers will be assessed only at the US sites and therefore the available sample size for these analyses will be 102 women (68 in the study IVR arm and 34 in the no IVR arm). A sample size of 102 women with a 2:1 randomization will allow detection of a medium effect size of 0.59 with 80% power in comparing quantitative levels between arms.

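### The supplementary between-arm test on change in Nugent score should adjust for the enrollment score; unadjusted, it needs roughly 26-44% more women for the same precision

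*Protocol*

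**What the plan says.** The formal flora comparison in Protocol Section 10.8.3 is a Fisher exact test on shifts between normal and abnormal Nugent categories. The section then says that "this analysis will be supplemented by an analysis using the change from baseline in Nugent score for each woman", and names the test: "Comparison for differences in change from baseline between arms will be assessed by using an unpaired t-test or a Mann-Whitney test", the second being for change scores that do not suit a t-test. No enrollment covariate is named. A Gram stain is scheduled for every woman at enrollment and at each follow-up visit (Sections 7.2 to 7.4, Appendix I).

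Section 10.4.4 gives the planning figures. From a sample of 1016 women, "28.4% of women with a normal Nugent score at enrollment had an abnormal Nugent score 4 months later" and "32.8% of women with an abnormal Nugent score at enrollment had a normal Nugent score 4 months later". From these, "we are estimating the proportion of changes in Nugent scores from enrollment to week 12 at 30% in the no IVR arm", in both directions, and "we are estimating that 55% and 45% of women will be normal and abnormal, respectively, at enrollment".

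For quantitative cultures, available at the US sites only (68 versus 34 women), the same section says the sample "will allow detection of a medium effect size of 0.59 with 80% power in comparing quantitative levels between arms". No adjustment for the enrollment level is mentioned.

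Section 10.5 stratifies randomization by site. Section 10.8.2 lists linear regression among the general methods but names no covariates.

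**The concern.** Subtracting the enrollment score gives it a fixed weight of one. Unless the regression slope of follow-up on enrollment really is one, that weight is wrong and the comparison carries avoidable variance. Regression estimates the weight from the data.

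Section 2.7.2 treats documentation of flora changes as an important part of confirming the ring's safety. The shift comparisons are powered only for differences of 25 and 28 percentage points, so the analysis of the score itself is where a smaller shift might be seen. Lost precision there makes a real shift easier to miss.

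**Working it through.** **Inputs.** All are from Protocol Section 10.4.4: enrollment split 55% normal and 45% abnormal; observed transitions 28.4% and 32.8%; planning transitions 30% and 30%; 68 versus 34 US women for cultures. The overall arm sizes of 168 and 84 are from Section 10.4.1. Assumptions: two-sided 5% tests (not stated for these comparisons, but they reproduce the plan's figures) and equal standard deviations at both visits.

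**1. The plan's own figures.** For cultures, the detectable effect at 80% power is (1.960 + 0.842) × √(1/34 + 1/68) = 2.802 × 0.2100 = 0.588 SD, or 0.594 with the t distribution. The stated 0.59 is reproduced. For the shift comparisons, 46 versus 92 women at 30% versus 55% gives 80.6% power, and 38 versus 76 at 30% versus 58% gives 82.0%. These also agree.

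**2. The correlation implied by the transition figures.**
- Observed rates: abnormal at both visits = 0.45 × 0.672 = 0.3024. Abnormal at follow-up = 0.3024 + 0.55 × 0.284 = 0.4586. Phi = (0.3024 − 0.45 × 0.4586) / √(0.45 × 0.55 × 0.4586 × 0.5414) = 0.0960 / 0.2479 = 0.39.
- Planning rates (30% both ways): abnormal at both visits = 0.315, abnormal at follow-up = 0.48, phi = (0.315 − 0.216) / 0.2486 = 0.40.
- Tetrachoric correlation of the same tables, as a proxy for the score underlying the two categories: 0.57 and 0.59.

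**3. Relative variance of the arm difference.** Take follow-up only as 1. The change score has 2(1 − r) and ANCOVA has 1 − r², so ANCOVA divided by change = (1 + r)/2. The direction does not rest on equal standard deviations. In general the change-score variance exceeds the ANCOVA variance by (σ₁ − rσ₂)², where σ₁ and σ₂ are the enrollment and follow-up SDs, and this is never negative.

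| r | Change | ANCOVA | ANCOVA / change | Extra women for change test |
|---|---|---|---|---|
| 0.3 | 1.40 | 0.91 | 0.65 | 54% |
| 0.387 | 1.23 | 0.85 | 0.69 | 44% |
| 0.398 | 1.20 | 0.84 | 0.70 | 43% |
| 0.5 | 1.00 | 0.75 | 0.75 | 33% |
| 0.572 | 0.86 | 0.67 | 0.79 | 27% |
| 0.588 | 0.82 | 0.65 | 0.79 | 26% |
| 0.7 | 0.60 | 0.51 | 0.85 | 18% |

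**4. What this means with 168 versus 84 women.** At r of 0.39-0.40, the change-score test on 252 women is as precise as ANCOVA on about 175. The detectable difference is 0.41 SD for change and 0.34-0.35 SD for ANCOVA. At r of 0.57-0.59 the equivalent number is about 200 women, and the detectable differences are 0.34-0.35 and 0.30-0.31 SD. An effect that the change-score test detects with 80% power would be detected by ANCOVA with about 92% power at the lower correlation and 88% at the higher.

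**5. Cultures.** The protocol gives no correlation for culture counts. If r were about 0.4 (an assumption), adjustment multiplies the detectable effect by √(1 − 0.16) = 0.917. That takes 0.588 to 0.54 SD (normal approximation) or 0.594 to 0.545 SD (t distribution). Power at 0.59 SD rises from 80% to about 86%.

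The variance formulas describe the t-test and least-squares regression. For the Mann-Whitney alternative they are only a guide.

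**The case against.** The best defence is that this is a small matter. The test is explicitly a supplement. The flora objective is descriptive (Section 3.2), no decision rule depends on the result, and an unpaired test on change is valid in a randomized trial. All of that stands, and it limits the weight of the point without removing it: the protocol names a specific test, and a more precise one uses data already collected.

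Several stronger readings are tempting but not supported.

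- *That the flora analyses ignore the enrollment value.* They do not. Section 10.4.4 plans the shift comparisons separately for women normal and women abnormal at enrollment, so they condition on enrollment category. The change score uses the enrollment value too, though inefficiently. For cultures, Section 10.8.3 also plans to compare changes of at least one log.
- *That subtracting the enrollment score makes matters worse than ignoring it.* This is true only for r below 0.5. Phi comes from a two-category split and probably understates the correlation of the 0-10 score. At 0.57-0.59 the change score beats follow-up alone (0.82-0.86 against 1).
- *That the behavioural comparisons omit the enrollment value.* The text says only that "The generalized estimation equation (GEE) method will be used to assess the difference of each measure between the two arms", accounting for within-subject correlation. It is silent on covariates, which a statistical analysis plan commonly supplies, and number of new partners is not asked at enrollment.
- *That chance imbalance is acute because there are only 34 US controls.* Those 34 belong to the cultures. Gram stains are read for the India site as well (Section 7.9), so the Nugent comparison has 84 controls. Chance imbalance under randomization costs precision and does not bias the comparison on average.
- *That week-12 biomarkers should be adjusted in the same way.* The cervical swabs for innate factors are scheduled at enrollment and week 16 only (Appendix I).

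**Conclusion.** The point holds for the supplementary Nugent test. Its direction is certain, because ANCOVA is more precise at any correlation below 1 when the SDs are equal, and never less precise in large samples. Its size is not certain: roughly 26-44% more women for the change-score test at the correlations implied by the protocol's transition figures, and 18-54% for r from 0.7 to 0.3.

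The size assumes equal standard deviations. It also assumes that unpublished four-month transition rates and a planning split of 55/45 carry over to a 12-week endpoint. Section 5.4 keeps out women with infections requiring treatment, including bacterial vaginosis, until treated, so r in this trial may differ. No single figure, including 44%, should be read as the protocol's own.

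The type I error of the test, the shift comparison and the primary safety and adherence endpoints are unaffected. For the US culture levels, Section 10.8.3 fixes no model. Adjustment there is a consistent extension, with a modest gain that rests on an assumed r.

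**What to change.** In Section 10.8.3, or in the statistical analysis plan with the protocol wording aligned, replace the unpaired test on change with a regression of the week-12 Nugent score on arm, with the enrollment score and site (the randomization stratum) as covariates. Name a rank-based or ordinal version in advance for use if the scores are not close to normal. Keep the shift comparison as planned. A mean change by arm can still be tabulated as description.

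Use the same model for log culture levels at the US sites, with the enrollment log count and site as covariates.

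The cost is a few sentences of analysis wording. No visit, specimen or sample size changes, because the enrollment Gram stain and flora swabs are already scheduled.
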